minutes post LPS. We define microglia activation reserve index (MARI) as the proportional increase in binding of PBR28, 180 minutes after the administration of the LPS:  $MARI = [(VT(LPS)-VT(baseline))/ VT(baseline)] \times 100$ . In a previous study, we demonstrated the feasibility and robustness of this technique by applying this methodology to 8 healthy volunteers showing 30-60% increase in PBR28 binding after LPS administration (10). We predict increased MARI in patients with early AD compared to cognitively normal aged matched individuals. Given that we also have data from young healthy individuals from our earlier study, we can explore whether the microglia activation reserve index is increased in microglia with aging (which we predict to be the case). We can gauge also whether the changes in MARI in AD represent incremental increases compared to normal aging or that a significant dysregulation of innate immunity occurs in AD. With this experiment we aim to:

Aim - Examine the differences in the capacity to activate microglia in patients with AD compared to age-comparable cognitively normal subjects and younger healthy controls.

Hypothesis: In early AD the innate immune response becomes more reactive to PAMPs and DAMPs compared to those with normal cognition.

Our primary outcome is MARI (calculated in the parietal ROIs) in AD patients compared to elderly controls. We will use 7 AD and 7 comparably aged cognitively normal successfully scanned subjects to calculate the microglial activation reserve index. We expect significant differences between the two groups suggesting increased reactivity of the microglia in AD. The reverse would suggest a burn-out phenomenon which we expect to occur in a later stage of the disease but not in our study cohort. This result would be an exciting one suggesting at least one mechanism by which some patients with significant amyloid load have progressive dementia while comparable others are either cognitively normal or have stable MCI. It will also suggest avenues for intervention in amyloid positive MCIs to prevent progression to Alzheimer's dementia. Our exploratory analysis will include:

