- a) Effects of aging on MARI: We will evaluate the effects of aging on MARI. Comparisons will be made for MARI between cognitively normal elderly and the 8 healthy individual to whom we applied this protocol in an earlier study. The reactivity of microglia is reported to increase with age (11) and so we expect MARI to increase in the cognitively normal elderly. However, we expect the differences between the young and elderly cognitively normal subjects to be small relative to the comparison of AD and elderly normal controls.
- b) Effects of amyloid on MARI: We will look at the relationship of regional and global amyloid load to MARI. The presence of a relationship suggests that one of the reasons for increased microglial reactivity might be interactions of microglia with pathologic amyloid.
- c) Effects of MARI on cognition: We will explore whether MARI would correlate with measure of disease stage, with higher MARIs associated with worse neuropsychological score and more severe disease. We will look for correlations between MARI and the individual neuropsychological scores. This would determine if disease severity is correlated with microglial activation reserve.

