For this study we choose PBR28. Amongst TSPO ligands PBR28 seems to have the most desirable characteristics for inflammatory imaging in AD: It has very high affinity for TSPO and an excellent signal-to-noise ratio (96). The main problem with this ligand, shared by all TSPO ligands except PK11195, is the variable specific binding of PBR28 due to TSPO gene polymorphism (rs6971) (97,98). The method used for adjusting for this fact involves genotyping TSPO (or using a competitive binding assay) and excluding low affinity binders. For the mixed (heterozygous for the polymorphism) and high affinity binders compensatory changes can be made in calculating binding (6,99–101). Four studies thus far have used PBR28 in Alzheimer's disease but only one attempted to directly compare AD patients with MCI and cognitively normal patients. This particular study was conducted at the molecular imaging branch of National Institute of Mental Health7, which compared 19 AD, 10 MCI and 13 amyloid negative controls for TSPO binding. Patients with AD showed increased binding especially in the temporal and parietal lobes. Additionally, there were correlations between TSPO binding and neuropsychological as well as volumetric parameters. Another group (102) performed a genome wide association study of longitudinal accumulation of amyloid independent of APOE status. They found carriers of IL1RAP rs12053868 had faster progression and worse atrophy compared to non-carriers. In a different cohort the same gene polymorphism was associated with lower cortical binding of 11C-PBR28 suggesting a protective role for inflammation. In yet another study (103), the same group showed a relationship between PBR28 binding and PPAR1 polymorphism, and they inversely correlated PBR28 and cortical atrophy.

Innate immunity, mediated by microglia, plays an important role in the pathogenesis of Alzheimer's disease. As discussed above, several genes implicated in microglial function are risk factors for late onset AD. TREM2 one of the genes with the highest odds ratios for AD risk, codes for a membrane protein which is involved in the interaction of

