### Preliminary Results and Demonstration of Plausibility

To calculate the test retest reliability, we obtained two PBR28 scans (107), on average 1.4 weeks apart, on 4 clinically stable relapsing-remitting MS subjects (age  $41 \pm 7$  years, two men/two women) and four healthy control (age  $42 \pm 8$  years, 2 two men/two women), matched for translocator protein genotype for test. Mean test VT values ( $ml cm^{-3}$ ) were  $3.9 \pm 1.4$  in the whole brain gray matter (GM),  $3.6 \pm 1.2$  in the whole brain white matter (WM) or normal-appearing white matter (NAWM), and  $3.3 \pm 0.6$  in MS WM lesions; mean retest VT values were  $3.7 \pm 1.0$  in GM,  $3.3 \pm 0.9$  in WM/NAWM, and  $3.3 \pm 0.7$  in MS lesions. Test-retest results showed a mean absolute TRV ranging from 7 to 9 % across GM, WM/NAWM, and MS lesions. Another MS subject (age 41 years, male) with clinical and radiological activity was studied for lesion detectability.

[figure not shown]

Figure 1 – The top row contains three slices of a gadolinium enhanced T1, showing a white matter lesion in the right mesial frontal subcortex. The bottom row shows the same three sections with PBR28 spatially corresponding to the exacerbating lesion. (Figure-1).

We thus showed that PBR28 scanning has good test-retest reproducibility in humans and can localize focal inflammation. To show its utility in imaging more diffuse inflammation, we employed the primate endotoxemia model (108). Six female baboons (*Papio anubis*) were scanned before and at 1h and/or 4h and/or 22 h after intravenous administration of *E. coli* lipopolysaccharide (LPS; 0.1mg/kg), which induces systemic inflammation (figure 2). LPS administration increased [(11)C]PBR28 binding ( $F(3,6)=5.1$ ,  $p=.043$ ) with a  $29 \pm 16\%$  increase at 1h ( $n=4$ ) and a 62

[figure not shown]

Figure 2 – A representative baboon brain. A) MRI of brain. B) This is the baseline image showing sparse inflammation. C) Increased inflammation 1 hour post injection of LPS. D) It reaches a maximum 4 hours post injection.

$\pm 34\%$  increase at 4h (n=3) post-LPS106. Significantly immunohistochemistry from one baboon showed immunoreactivity exclusively in microglia and not in astrocytes.

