**TSPO gene polymorphism:**

We will genotype the patient with regards to rs6971 polymorphism on the TSPO gene to exclude those who are homozygous (low affinity binders). For this we will use 50 ng of genomic DNA, amplified with PCR reaction. Control plasmids encoding for high affinity binders (C/C) and low affinity binding (T/T) will be used as controls. For the heterozygote i.e. mixed affinity binders a 1:1 mixture of both will be used.

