**PET Imaging of TSPO in AD**

We will compare PBR28 binding site availability in brain regions of 7 living human subjects who have AD with that in 7 age-matched healthy controls by using the ligand  $^{11}\text{C}$ -PBR28 and PET. Dose of LPS (see below) will be administered intravenously and the subject will be reimaged at 180 minutes after the injection. Considering possible failures in scans, a total of 16 patients will be studied in 2 groups, cognitive normal AND amyloid negative versus clinical criteria for mild AD and amyloid positive to reach our goal of 7 successfully scanned subject for each group. The detailed protocol may be found

09/29/12 Version 13

in our previous publication (109). We expect that 20-30% of cognitively normal participants who receive amyloid scans under this protocol will be amyloid positive. Therefore, we will enroll up to 10 participants in the cognitively normal cohort to attain the goal of 7 participants who are cognitively normal AND amyloid negative.

Primary Outcome:

The 16 enrolled subjects will have C-PBR28 using the bolus/infusion method. Measurements will be made at baseline and 180 minutes after the injection of LPS. We will measure Total Volume of Distribution (VT) for 12 brain regions defined by MRI scan, as described (111). All primary outcomes will use the parietal ROI for calculations of both baseline activation and microglial activation reserve. For our primary outcomes we will choose the microglia activation reserve index defined as MARI =  $[(VT(LPS)-VT(\text{baseline}))/ VT(\text{baseline})] \times 100$ . In the NIMH study the greatest difference in the regional PBR28 binding between AD and cognitively normal subjects was found in the parietal lobe (7). We also found the greatest microglia activation reserve index in the parietal lobe when we applied our paradigm to young healthy controls (109). Other ROIs will be used in secondary analyses.

Statistical Considerations and Sample Size:

Several comparisons of C-PBR28 VT brain level and microglia activation reserve index in the parietal lobe will be made using Student T-test to test for a difference between group means: young healthy group vs. elderly cognitively normal, as well as AD vs. elderly cognitively normal.

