**Primary Outcome:**

The 16 enrolled subjects will have C-PBR28 using the bolus/infusion method. Measurements will be made at baseline and 180 minutes after the injection of LPS. We will measure Total Volume of Distribution (VT) for 12 brain regions defined by MRI scan, as described (111). All primary outcomes will use the parietal ROI for calculations of both baseline activation and microglial activation reserve. For our primary outcomes we will choose the microglia activation reserve index defined as MARI = [(VT(LPS)-VT(baseline))/ VT(baseline))] X %100. In the NIMH study the greatest difference in the regional PBR28 binding between AD and cognitively normal subjects was found in the parietal lobe (7). We also found the greatest microglia activation reserve index in the parietal lobe when we applied our paradigm to young healthy controls (109). Other ROIs will be used in secondary analyses.

Statistical Considerations and Sample Size: Several comparisons of C-PBR28 VT brain level and microglia activation reserve index in the parietal lobe will be made using Student T-test to test for a difference between group means: young healthy group vs. elderly cognitively normal, as well as AD vs. elderly cognitively normal. Although this is intended as a pilot study we have performed some basic power analyses. For the comparison of baseline activation in AD vs. aged matched cognitively normal subjects based on standard deviations derived from Kreisel (7) and our own previous studies (107,109,111), using an alpha of 0.05 and power of 0.80, our study is powered to detect an effect size of > 1.6 which is not far off from the findings in the NIMH study. For the comparison of percentage post-LPS change from baseline in AD and NC groups we are powered to detect an effect size of more than 2.

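### TSPO genotype is collected but used only to exclude low binders; the t-tests pool high- and mixed-affinity binders, which costs precision for baseline VT and has an uncertain effect on MARI

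*Combined protocol and SAP*

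**What the plan says.** Section V.2 (Background) singles out, as the chief drawback of the tracer, "the variable specific binding of PBR28 due to TSPO gene polymorphism (rs6971"). It describes a two-part remedy: leave out low-affinity binders, and correct the binding estimate for the remaining mixed and high binders. The second part is mentioned as possible, without a method.

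The operational text carries out only the first part. Under TSPO gene polymorphism in the Research Plan: "We will genotype the patient with regards to rs6971 polymorphism on the TSPO gene to exclude those who are homozygous (low affinity binders"). Section V.4 (Genetic Testing) and exclusion criterion 20 give the same use.

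The analysis text appears twice, under PET Imaging of TSPO in AD and again under Statistical Considerations. Comparisons of parietal VT and MARI "will be made using Student T-test to test for a difference between group means". No covariate, stratum, matching rule or corrected VT is named. The primary outcome is parietal MARI in AD against elderly controls. Section V.1 says "We will use 7 AD and 7 comparably aged cognitively normal successfully scanned subjects"; for the ageing question, "Comparisons will be made for MARI between cognitively normal elderly and the 8 healthy individual" from the earlier LPS study.

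The team has treated genotype as important before. Its test-retest subjects were "matched for translocator protein genotype", and the legend of Figure 3B shows VT in the young LPS cohort separately for high- and mixed-affinity binders.

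**The concern.** High and mixed binders differ in measured binding for a reason unrelated to microglial activation. A t-test that ignores this leaves the genotype difference in the error term. If the two groups of 7 happen to contain different numbers of mixed binders, part of the observed group difference is a genotype difference. The groups are diagnostic, not randomised, and the young comparator is a fixed historical set of 8 whose genotype mix cannot now be changed. The information needed to deal with this is already collected before scanning.

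At stake are the precision of the baseline VT comparison and the interpretation of any single-sample difference when genotype counts are unequal. There is also a risk that the choice between an adjusted and an unadjusted result is made after the data are seen.

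**Working it through.** **1. The plan's own figure.** Inputs: 7 per group, "using an alpha of 0.05 and power of 0.80"; sidedness is not stated, so two-sided is assumed. For a two-sample t-test with 12 df (noncentral t), the detectable standardised difference at 80% power is 1.63. Power is 78.5% at 1.6 and 79.4% at 1.62. The stated 1.6 for baseline VT reproduces to rounding.

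**2. How common mixed binders will be.** Exclusion criterion 20 puts low binders below 10%. Under Hardy-Weinberg (assumption), with q the low-affinity allele frequency, the mixed share of eligible subjects is 2q/(1+q).
- 10% low binders: q = 0.316, share 0.48.
- 5% low binders: q = 0.224, share 0.37.

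I use a slightly wider range, 30-50% mixed (50-70% high).

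**3. Chance imbalance, 7 v 7.** Counts of mixed binders are independent Binomial(7, p).
- Counts differ by 2 or more: 0.38 at p = 0.3, 0.42 at p = 0.5.
- Counts differ by 3 or more: 0.14 at p = 0.3, 0.18 at p = 0.5.

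A difference of k subjects moves the group VT contrast by k/7 of the genotype shift. For k = 3 and shifts of 1 and 2 within-genotype SD, that is 3/7 = 0.43 and 6/7 = 0.86 SD. In VT units, take the grey-matter means of 3.7-3.9 ml/cm3 in Preliminary Results, an assumed high:mixed VT ratio of 1.2-1.5 and a 50:50 mix. A 2-subject imbalance then moves the contrast by about 0.2-0.45 ml/cm3. For example, 3.9/1.25 = 3.12; 0.5 x 3.12 = 1.56; 2/7 x 1.56 = 0.45.

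Averaged over samples, with genotype unrelated to group, the mean bias is zero and simulated type I error is 4.8-5.3%. Only within samples where the counts differ by 3 does it rise, to about 8-9% (shift 1 SD) or 12-13% (shift 2 SD).

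**4. Power for baseline VT.** With a shift of s within-genotype SD, the pooled variance is 1 + s²p(1-p), and a true difference of 1.62 within-genotype SD shrinks to 1.62/√(1 + s²p(1-p)). At p = 0.5:

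| Shift s | Variance factor | Effective d | t-test power | Group + genotype model (simulated) |
|---|---|---|---|---|
| 0 | 1.00 | 1.62 | 0.79 | 0.75 |
| 1 | 1.25 | 1.45 | 0.70 | 0.75 |
| 1.5 | 1.56 | 1.30 | 0.61 | 0.75 |
| 2 | 2.00 | 1.15 | 0.50 | 0.75 |

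The shift is an assumption. A VT ratio of 1.2-1.5, a within-genotype CV of 20-30% of mean VT and a mixed share of 35-48% give s from 0.2/(0.3 x 1.13) = 0.59 to 0.5/(0.2 x 1.26) = 1.98. Over that grid, at d = 1.63, t-test power is 51-77% and adjusted power about 76%. At the weak end adjustment gains nothing.

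**5. MARI.** Write VT as non-displaceable plus specific signal. If LPS raises specific signal by a fraction r, MARI = r x specific/(specific + non-displaceable).
- No non-displaceable signal: MARI = r for both genotypes, so the genotype effect cancels.
- Illustration with r = 60%, non-displaceable 1, specific 3 (high) and 1.5 (mixed), all assumed: 0.6 x 3/4 = 45% against 0.6 x 1.5/2.5 = 36%, a gap of 9 points.
- Wider assumptions (non-displaceable 0-40% of VT in high binders, specific binding halved in mixed binders, MARI 30-60% in high binders): gap 0-17 points; a 2-subject imbalance moves the group difference by 0-5 points.

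Scale for the 9-point gap: the reported mean absolute test-retest variability of 7-9% (not parietal) implies, for normal errors, an SD of 7/0.798 = 8.8% to 9/0.798 = 11.3% for the scan-to-scan change. Multiplied by a post/baseline ratio of about 1.4, that is roughly 12-16 MARI points before any between-subject spread. So 9 points is at most about 0.6-0.7 SD. At 0.6 SD, power is 0.76 unadjusted and 0.75 adjusted.

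**The case against.** Four arguments on the other side carry weight.

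- **Bias.** A reader might infer that the t-tests are biased. The documents do not support that: nothing suggests that genotype mix differs by diagnosis, and without such a link there is no systematic bias or type I inflation. What stands is chance imbalance in one small sample.
- **The primary outcome.** A reader might also carry the VT power figures over to MARI. MARI is self-normalised and the documents give no MARI by genotype, so those figures do not transfer. Cancellation cannot be assumed either, because the Background places the genotype effect in specific binding while the plan measures total VT.
- **The units of the 1.6.** The SDs come from the cited NIMH study and the team's earlier studies, and the LPS cohort contained both genotypes. If those SDs pool genotypes, the variance is already in the 1.6 and t-test power there stays near 0.79-0.80. The plan would not then be underpowered against its own statement; adjustment would serve to improve precision.
- **Correction elsewhere.** The Background mentions compensation, and the cited methods papers might apply it when VT is computed. That does not fill the gap: the mention is background, gives no method, and the analysis as written pools the two genotypes.

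An additive genotype term is also only approximate. If disease raises specific binding proportionally, the VT difference is larger in high binders, and one term does not capture that interaction. With 7 per group it is still a reasonable first-order adjustment.

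**Conclusion.** The point holds mainly for baseline VT. The plan identifies genotype as a major source of variation, collects it, and then leaves it out of the analysis of the subjects who remain. That adds variance and exposes the 7 v 7 comparison, and the comparison with the fixed young group, to chance imbalance.

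The power loss (about 0.70-0.50 unadjusted against 0.75 adjusted) rests on an assumed genotype shift of 1-2 SD and on reading the 1.62 in within-genotype SD units; the documents settle neither. The imbalance probabilities rest only on the assumed 50-70% share of high binders and on genotype being unrelated to group.

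For MARI the size is unknown. It is nil if genotype acts multiplicatively on VT and partial if VT contains non-displaceable signal, and adjustment may bring no gain in power. Calling the primary comparison biased or underpowered on this ground would go beyond the documents. The matter is worth settling in advance because the data are already collected and the change is one of wording.

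**What to change.** In both copies of the analysis text (under PET Imaging of TSPO in AD and under Statistical Considerations):

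- **Baseline VT:** analyse parietal VT with a linear model containing group and genotype (high or mixed). Report the adjusted group difference with its 95% CI, and the unadjusted t-test as a sensitivity analysis.
- **MARI:** keep the t-test, and report the same genotype-adjusted model beside it as a prespecified sensitivity analysis.
- **Reporting:** give genotype counts by group, including the 8 young subjects.

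Cost: no new procedure or subject. The model uses one degree of freedom (11 instead of 12), about 4-5 points of power (roughly 0.80 to 0.75) if genotype turns out not to matter.

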### **SECTION VII: RECRUITMENT/CONSENT AND ASSENT PROCEDURES**

**1. Targeted Enrollment: Give the number of subjects:**

- a. targeted for enrollment at Yale for this protocol up to 10 cognitively normal subjects and 10 MCI subjects. This is larger than the 16 subjects discussed above because we may need to enroll up to 3 additional subjects in each cohort to identify 7 cognitively normal AND amyloid negative and two additional to identify 7 MCI and amyloid positive subjects (total 9) due to possible failures in completing the study.
- b. If this is a multi-site study, give the total number of subjects targeted across all sites

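### The plan gives the primary endpoint (MARI) a detectable effect of more than 2, but its only stated inputs give 1.63 SD; the error is conservative and needs restating

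*Combined protocol and SAP*

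**What the plan says.** The text headed Statistical Considerations and Sample Size appears twice in Section V: in the Research Plan, and again after the safety monitoring plan. Group comparisons will be "made using Student T-test to test for a difference between group means". For baseline PBR28 binding in AD patients against controls, the inputs are given: "using an alpha of 0.05 and power of 0.80, our study is powered to detect an effect size of" more than 1.6. The next sentence turns to MARI, the percentage rise in binding after LPS: "percentage post-LPS change from baseline in AD and NC groups we are powered to detect an effect size of more than 2". That sentence does not repeat alpha or power, define effect size or give an SD. The Statement of Purpose makes parietal MARI the primary outcome and sets the analysed sample at 7 AD patients and 7 controls.

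On control numbers, PET Imaging of TSPO in AD states: "We expect that 20-30% of cognitively normal participants who receive amyloid scans under this protocol will be amyloid positive". It therefore plans to "enroll up to 10 participants in the cognitively normal cohort to attain the goal of 7 participants who are cognitively normal AND amyloid negative". The same section allows 16 subjects for 14 usable ones because scans may fail, without giving a failure rate. Section VII.1 adds that "we may need to enroll up to 3 additional subjects in each cohort". For the patient cohort it gives 10, and then two extra for a total of 9.

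**The concern.** A standardised detectable difference depends on group sizes, alpha, sidedness and power. The SD of the measure cancels out. Baseline binding and MARI are to be compared between the same two groups with the same test, so two different standardised figures cannot both be right unless some input changes, and no change is stated.

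The figure that fails is the one for the primary endpoint. Pitfalls and Limitations says the study is to supply preliminary data for a larger project. A reader designing that project would take from this text the wrong sensitivity for MARI, and would find no SD from which to correct it.

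A related question is whether 7 controls will be available at all, since the cap of 10 appears to be sized for amyloid status alone and not also for failed scans.

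**Working it through.** **Inputs.** t-test, alpha 0.05 and power 0.80 (Statistical Considerations and Sample Size); 7 per group (Statement of Purpose; PET Imaging of TSPO in AD). Sidedness is not stated; two-sided is taken, with one-sided also shown.

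**Step 1: reproduce the baseline figure.** With n1 = n2 = 7, df = 12 and the critical value is t = 2.179. The noncentrality is d × sqrt(n1·n2/(n1+n2)) = d × sqrt(49/14) = 1.871d. Solving the noncentral t for 80% power gives d = 1.632. The stated figure of more than 1.6 is reproduced.

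**Step 2: the MARI figure.** The same inputs give the same answer, 1.63 SD. At d = 2 the noncentrality is 1.871 × 2 = 3.742 and power is 92.9%.

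**Step 3: what would give about 2?** Each row is two-sided unless noted.

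| Inputs | Detectable d |
|---|---|
| 7 v 7, alpha 0.05, power 0.80 | 1.63 |
| the same, one-sided | 1.41 |
| the same, normal approximation | 1.50 |
| 7 v 7, alpha 0.05, power 0.90 | 1.89 |
| 7 v 7, alpha 0.05, power 0.95 | 2.10 |
| 7 v 7, alpha 0.025, power 0.80 | 1.85 |
| 7 v 7, alpha about 0.015, power 0.80 | 2.00 |
| 5 v 5, alpha 0.05, power 0.80 | 2.02 |

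None of the rows that reach 2 uses inputs the plan states for this comparison.

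**Step 4: precision and loss of controls.** The 95% confidence interval half-width at 7 v 7 is 2.179 × sqrt(2/7) = 1.16 SD. With 7 patients and fewer controls, the detectable d is 1.71 (6 controls), 1.82 (5) and 1.97 (4).

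**Step 5: control yield (conditional).** Assume that all 10 controls enter with unknown amyloid status, that only amyloid-negative controls count, and that scan failure is independent of amyloid status. Each control is then usable with probability p = (1 − amyloid-positive rate) × (1 − scan-failure rate), and the number usable is Binomial(10, p). The 20-30% rate is the plan's. The 12.5% failure rate is inferred: 2 of 16.

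| Amyloid positive | No scan failure: p, P(at least 7) | 12.5% failure: p, P(at least 7) |
|---|---|---|
| 20% | 0.80, 87.9% | 0.70, 65.0% |
| 25% | 0.75, 77.6% | 0.656, 53.1% |
| 30% | 0.70, 65.0% | 0.6125, 41.4% |

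The expected number usable is 10p: 7 to 8 without failures, and 6.1 to 7.0 with them.

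**The case against.** The strongest reply is that the statement is literally true. A study with 93% power at 2 SD is powered to detect effects above 2, and this remains so with only 4 usable controls (power 81%). The plan calls itself a pilot and lists small numbers as a limitation. This stands as regards direction and consequence. A reader might infer that the trial is underpowered for its primary endpoint; the documents do not support that. What remains is that the figure is not the detectable effect at the stated inputs, and that the plan reports a lower sensitivity than it has. A true difference of 1.75 SD would have 85% power, yet the text suggests it is out of reach.

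It can also be said that the MARI sentence does not restate alpha or power or define effect size, so other inputs may have been used. That is possible, and it is why the fix offers the alternative of stating them.

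A reader might go further and say that the whole sample-size paragraph fails. It does not: its baseline figure reproduces.

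A reader might also convert the result to MARI points from the line "Test-retest results showed a mean absolute TRV ranging from 7 to 9 % across GM". The documents do not support this. That variability comes from grey matter, white matter and MS lesions, not from the parietal region, and takes no account of the rise after LPS. The baboon data offer an SD of 16 at 1 hour and 34 at 4 hours, with no basis for choosing between them. No MARI SD is given.

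On controls, several points stand. The 41-65% range needs a failure rate that the plan does not state. The radiation-risk section allows a repeat tracer infusion after an unsuccessful scan, so a failed scan need not lose the subject. The 20-30% rate applies only to those scanned for amyloid under this protocol. The Statement of Purpose and the inclusion criteria do not require amyloid-negative controls, and the section on PET for amyloid has controls scanned whatever their result. If amyloid-positive controls counted, P(at least 7 of 10) at 12.5% failure would be 97%. Against that, PET Imaging of TSPO in AD and Section VII.1 do make amyloid-negative controls the target, so the sections disagree.

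The gap between 16 and the larger enrolment target is not a contradiction: Section VII.1 explains it by the extra enrolment needed.

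**Conclusion.** The MARI figure is wrong as written. At 7 v 7, two-sided alpha 0.05 and 80% power, the detectable difference is 1.63 SD, not more than 2. This assumes that effect size means a standardised mean difference and that the stated alpha and power carry over to MARI. The error is conservative and does not bear on whether the trial can go ahead as sized.

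The control-yield point is secondary and conditional. On the plan's amyloid rate alone, the cap of 10 reaches 7 amyloid-negative controls with probability 65-88%. It becomes 41-65% only if about 12.5% of scans are also lost and not repeated. A reader might infer that a shortfall is more likely than not; that follows only at the 30% end with the inferred failure rate added. Losing one control would move the detectable difference from 1.63 to 1.71 SD, a small change.

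Two inconsistencies remain: whether controls must be amyloid negative to count, and 10 against 9 patients within Section VII.1.

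**What to change.** In both copies of the sample-size text:

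- Give one detectable difference for baseline binding and for MARI: 1.63 SD at 7 v 7, two-sided alpha 0.05, 80% power (1.71 SD at 7 v 6). If different inputs were meant for MARI, state them.
- State sidedness, define effect size, and give the MARI SD assumed with its source.
- Add the expected 95% confidence interval half-width, 1.16 SD, which is the more useful quantity for a pilot.

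Elsewhere:

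- State the expected yield from 10 controls and the scan-failure rate assumed.
- Reconcile PET Imaging of TSPO in AD and Section VII.1, which count amyloid-negative controls, with the Statement of Purpose, the section on PET for amyloid and the inclusion criteria, which do not require amyloid negativity.
- Settle the patient count of 10 or 9 in Section VII.1.

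The cost is wording only. Sample size and procedures do not change. The stated sensitivity for MARI improves, and the expected control count is shown to be slightly less favourable than the text now suggests.
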